Globally, pneumonia accounts for 16% of all deaths of children under 5 years oldⁱ. In sub-Saharan African (SSA) countries it causes approximately 750 000 child deaths per year in. In Mali, about 900,000 pneumonia episodes occur in children under 5 years of age annually, leading to almost 8,000 deaths. Pneumonia accounts for 2% of under-five deaths in Mali, but only 38% of children under five presenting with symptoms of pneumonia are taken to an appropriate health provider. In line with the World Health Organization (WHO) guidelines, increasingly, the first point of contact with the health care system for people seeking care for pneumonia symptoms is through community health care workers (CHWs)ⁱⁱⁱ. Aware that access to accurate diagnosis, treatment and appropriate referral determines a child's survival the Mali Ministry of Health (MoH) introduced Integrated Community Case Management (iCCM) in 2007, authorizing community health workers (CHWs) to diagnose and treat pneumonia, malaria, diarrhoea and malnutrition in children under five. Research has suggested that community case management of pneumonia, if properly implemented, could reduce under-five deaths from pneumonia by 70% v.

In 2012, WHO and UNICEF published a joint statement that supported iCCM as "an essential strategy that can both foster equity and contribute to sustained reduction in child mortality" and identified fast breathing as the key presenting symptom for diagnosing and treating pneumonia using the iCCM strategy i. WHO has set the threshold for respiratory rate (respiratory rate per minute) in infants less than 2 months at a respiratory rate of 60 per minute, for children 2 to 12 months at a respiratory rate of 50 per minute and for children 1 to 5 years at a respiratory rate of 40 per minute in its Integrated Management of Childhood Illness (IMCI) handbook widely used as the technical guidelines at the community level of care iii. Studies demonstrate that there is evidence to show that, when well-trained, CHWs can adequately manage pneumonia cases at the community level ix. However, when training is deficient CHWs' skills in measuring respiratory rates and accurately classifying pneumonia remain a challengex xi xii.

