In Mali, as part of their basic training, CHWs are trained to detect suspected pneumonia cases using video, practice sessions and their basic training manual. Algorithms used for diagnosis developed in the 1980s include assessing danger signs in children with a cough, counting respiratory rates, and observing chest in drawing to classify respiratory illness^{xiii}. These algorithms correspond with WHO's definition of presenting symptoms for pneumonia: cough and/or difficult breathing, with or without fever, the presence of either fast breathing or lower chest wall in-drawing where the child's chest moves in or retracts during inhalation.^{xiv} Because counting respiratory rate by observing the chest, by using a stethoscope or putting one's hand on an abdomen has been shown to have conflictive results^{xv}, both WHO and UNICEF recommend respiratory rate timers (RRTs) as a CHW diagnostic tool for pneumonia at the community level. There are several studies that have demonstrated that these tools can be used successfully by CHWs trained to use them^{xvi}. However, study results cautioned that for CHWs to be able to easily and accurately classify pneumonia cases additional practice in counting respiratory rates and simple job aides would be necessary^{xviii} x^{viii}.

Pneumonia is the number one cause of under-five deaths in Mali and case fatality rates can exceed 20%, but in 2013, of the 231,548 reported pneumonia cases only 20% were treated by CHWs. The quality of community health workers' diagnostic skills can influence how communities accept and use these workers. Poor competency in CHWs to correctly count respiratory rate, a key indicator for pneumonia detection, puts CHWs and their patients at risk of frequently misdiagnosing pneumonia and over prescription of antibiotics. The need for strong CHW competency to correctly count respiratory rate for a quick and accurate detection of pneumonia is evident.

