- Intervention Group A: CHWs trained in ChARM and using ChARM as a self-monitoring tool for 8 months while counting respiratory rate of children under 5 visually using a timer.
- Intervention Group B: CHWs trained in ChARM and using ChARM as a self-monitoring tool for 4 months while counting respiratory rate of children under 5 visually using a time; then discontinue using ChARM and continue to monitor the respiratory rate visually using a timer only for the remaining 4 months.
- Control Group C: CHWs who did not receive the ChARM training and will be monitoring the respiratory rate of children under 5 visually using a timer only, as per the MoH traditional training.

Throughout the study 3 independent Field Monitors will follow each group's participants in both Banamba and Koulikoro (i.e. one Field Monitor will follow 1/2 CHWs in Group A in Banamba and 1/2 CHWs in Group A Koulikoro; the Field Monitors responsible for Groups B and C will also follow one study group each, in both areas). The Field Monitors will be responsible for both testing the accuracy of the CHWs' ability to count respiratory rate and for collecting data during the study from the CHW reports and drug records. The Field Monitors will receive the same training as the CHWs in the Intervention Groups A and B, and additional training on data collection and observation protocol. The Field Monitor will test the CHWs' capacity to count respiratory rate during three intervals:

[figure not shown]
- Before the ChARM training
- 4 months after initiating the use of the ChARM device
- 8 months after initiating the use of the ChARM device (which corresponds to 4 months after the ChARM device will be discontinued for group B).

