CHWs randomized to intervention Groups A and B will be trained to use the ChARM device and in data collection requirements (filling out the self-monitoring sheet and getting consent from caregivers of children under 5). For the 4 months of Phase 1, CHWs in Intervention Groups A and B will count the respiratory rate of all children under five presenting with symptoms of cough or cold, using the timer and visual counting simultaneously with the ChARM device. Group C will count the respiratory rate using visual counting with the timer only.

Phase II: (4 months)

The second phase of the study will take place from July-November 2018. In the first month of this phase Field Monitor will retest CHWs for the 2nd time in all groups on their breath counting capacity against the ChARM automated reading and record results. The Field Monitor will also review the CHW monthly reports, consultation/referral forms, the drug supply forms, as well as the self-monitoring forms filled in by the CHWs. (Please see Annex 1 for a copy of all forms).

During Phase II, Group A will continue to count the respiratory rate of all children under five presenting with symptoms of cough and/or cold, simultaneously using the timer and visual counting and the ChARM device. However, once Group B is tested, the CHWs in that group will stop using ChARM and will start to count respiratory rate using only the visual counting measured by the timer. Group C will continue to count respiratory rate using only visual counting measured by the timer.

An interim analysis of the data from Phase II will be undertaken by an independent researcher (to be chosen by the DSMB) once testing has been completed in the three groups.

Phase III: (4 months)

This phase has three main activities. The first is the 3rd testing by Field Monitors of CHWs in all groups of their breath counting capacity against the ChARM automated reading and the recording of results. The Field Monitors will also review the CHW monthly reports, consultation/referral forms, the drug supply forms, as well as the self-monitoring forms filled in by the CHWs.

Once retested, CHWs in Group A will stop using ChARM and will start to count respiratory rate only using the visual counting measured by the timer. CHWs in Groups B and C will continue to count respiratory rate; only using visual counting measured by the timer.

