- 3. CHWs who do not have a device (a respiratory timer) to measure respiratory rate and who are not routinely counting respiratory rate to diagnose suspected pneumonia.
- 4. CHWs who did not complete the MoH basic training for CHWs provided through the 2016-2020 Strengthening Maternal, Newborn and Child Health program.

Enrollment

- 1. Approval from the Ministry of Health Mali and the Regional Directorate of Health, Koulikoro will be obtained to enroll CHWs providing iCCM services in the districts of Koulikoro and Banamba in the study.
- 2. Subsequently the local study coordinator will visit the MoH district level staff and share the letters of approval from the MoH and regional directorate with the facilities responsible for the CHWs working in the Banamba and Koulikoro districts to formalize the enrollment.
- 3. All consenting women and men seeking care from the CHW for a child under 5 presenting with symptoms of pneumonia (i.e. cough and/or cold) will be invited to provide consent and enroll in the study.

8. Intervention Groups

The intervention is a training in ChARM device offered to CHWs providing iCCM services to children under-five in the districts of Banamba and Koulikoro.

Once all CHWs in the two districts have been randomized into the three groups and had their breath counting skill tested using ChARM as a global measure, the CHWs randomized to Groups A and B will receive a 1-day training on the ChARM device. During the training, CHWs in intervention groups will learn how to use the ChARM device as a self-monitoring tool by comparing the respiratory rate they count visually when using the timer against ChARM's automated read-out during assessment of all children under-5 years presenting with symptoms of pneumonia (cough and/or cold). CHWs will be instructed to record the two measurements on the self-monitoring sheet and to continue to record the child's respiratory rates, treatment and referrals on the MoH forms they routinely fill out.

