Acute Respiratory Illness (ARI) Case fatality rate

Secondary outcomes:

Respiratory rate assessment accuracy

Proportion of pneumonia cases detected and treated by CHWs

Proportion of suspected severe pneumonia cases referred by CHWs to the CSCom

Proportion of suspected cases of pneumonia in the community who sought care from a CHW

Accuracy in drug management and procurement requests

Sample size:

48 clusters with average size of 50 suspected ARI cases per cluster per arm (over 8 months) are sufficient to detect a 30% reduction in the ARI case-fatality rate (from 20% at baseline), with 80% power and 5% significance. Differences in all secondary outcomes are powered above 80% within this sample size.

iCCM Curriculum Training: Intervention & Control sites

Participants: CHWs in Koulikoro and Banamba districts (n=148)

Time frame: Completed as part of CRC program implementation in Mali (December 2016 – August 2017)

Responsibility: CRC/MoH Mali Trainers

Training Material: Ministry of Health iCCM curriculum for CHWs -18-day curriculum including classroom instruction and hands on training.

Intervention Training: Intervention sites

Participants: CHWs in Koulikoro (n≅49) and Banamba (n≅49) districts.

Time Frame: After iCCM curriculum training; 9 months-1month for training CHWs in ChARM and 8 months for monitoring.

Responsibility: External Trainers and Study coordinator

- A. CHWs trained in ChARM and the self-monitoring data collection format.
- B. Submission of regular MoH monthly reports, consultation referral forms, drug supply forms.
- C. In-depth interviews for CHWs, Field Monitor and the Technical Director of Health Centres (Directeur Technique du Centre/CSCom) on their perception of ChARM tool and recommendations for future use as a teaching tool and/or scale up by the MoH.

Control Sites

CHWs in Koulikoro and Banamba districts (n=49)

Time frame: 8 months-including initial measurement of respiratory rate counts using a timer against ChARM's automated reading and subsequently repeating the measurement twice during the study.

- A. Pneumonia diagnosis as per usual practice of visually counting respiratory rate using a respiratory timer.
- B. Submission of regular monthly reports, consultation/referral reports and drug supply reports for review by Field Monitors.

12. Data Processing and analysis

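### The 80% power for ARI case fatality rests on an unsourced 20% baseline that conflicts with the protocol's own death and population counts

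*Protocol*

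**What the plan says.** ARI case fatality is the named primary outcome (Project Summary; Section 11, Outcomes). One sentence in Section 11 under Sample size justifies the numbers for it: 48 clusters per arm, averaging 50 suspected ARI cases over eight months, "are sufficient to detect a 30% reduction in the ARI case-fatality rate (from 20% at baseline), with 80% power and 5% significance". It does not state a source for the 20%, a sidedness, which arms are compared, or an intracluster correlation (ICC).

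The Background and Rationale gives national figures: "about 900,000 pneumonia episodes occur in children under 5 years of age annually, leading to almost 8,000 deaths". It also states: "Pneumonia is the number one cause of under-five deaths in Mali and case fatality rates can exceed 20" per cent. For 2013 it adds that "of the 231,548 reported pneumonia cases only 20% were treated by CHWs".

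The children who contribute cases are defined broadly. In Phase I (Section 6), CHWs in Groups A and B are to "count the respiratory rate of all children under five presenting with symptoms of cough or cold". Under Enrollment (Section 7), caregivers of a child "presenting with symptoms of pneumonia (i.e. cough and/or cold) will be invited to provide consent and enroll in the study".

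Figure II (Section 5) counts the under-fives covered by CHW sites in 2016: 18,301 in Banamba and 13,957 in Koulikoro.

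**The concern.** A statement that rates can go above 20% describes the upper end of a range. Section 11 uses the same number as the expected average among all suspected ARI cases that a CHW sees, a group defined by cough or cold and therefore wider than pneumonia. The national counts point to a rate more than twenty times lower.

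The baseline drives the power, because a 30% relative reduction in a rare outcome yields few deaths to compare. If the true rate is far below 20%, a null case-fatality result would say little, yet the stated 80% would invite ethics boards and readers to take it as evidence of no effect. The objective on counting accuracy does not depend on this baseline.

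**Working it through.** **Inputs.** Section 11: 48 × 50 = 2,400 cases per arm, so 7,200 in three arms; a fall from 20% to 0.7 × 20% = 14%; 5% significance. Background: 8,000 deaths, 900,000 episodes, 231,548 reported cases. Figure II: 18,301 + 13,957 = 32,258 covered under-fives. Sidedness, comparison and clustering are not stated, so a range of each is shown.

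**Formula.** Power = Φ{[(p1 − p2) − z·SE0] / SE1}, where SE0 = √[p̄(1 − p̄)(1/n1 + 1/n2)], SE1 = √[p1(1 − p1)/n1 + p2(1 − p2)/n2], and z is 1.960 (two-sided) or 1.645 (one-sided). For clustering, n is divided by 1 + 49 × ICC.

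**1. The plan's own figure.** Pairwise, two-sided, no clustering: (0.06 − 1.960 × 0.010844) / 0.010809 = 3.585, so power is 99.98%. It falls to exactly 80% at an ICC of about 0.059 (design effect 3.91, about 614 effective cases per arm). The stated 80% is therefore attainable at a 20% baseline. The question is the baseline.

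**2. Against the Background counts.** 8,000 / 900,000 = 0.89%. At 20%, 900,000 episodes would give 180,000 deaths, which is 22.5 times the stated figure.

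**3. Against Figure II.** 7,200 × 0.20 = 1,440 deaths in eight months without any effect, and 1,440 / 32,258 = 4.5% of all covered under-fives. If both intervention arms had the full 30% reduction, deaths would be 480 + 336 + 336 = 1,152, or 3.6%. Set against the Background's annual national total, two districts would supply 1,440 / 8,000 = 18%, or 1,152 / 8,000 = 14%, in eight months. The 4.5% and 3.6% figures do not use the 0.89% ratio.

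**4. Power at 0.89% (falling to 0.62%).** Expected deaths are about 21 in the control arm and 15 in an intervention arm, where the plan assumes 480 and 336.
- Pairwise, two-sided: (0.002667 − 1.960 × 0.0025) / 0.0025 = −0.893, giving 18.6%.
- A+B against C (4,800 against 2,400), one-sided: (0.002667 − 1.645 × 0.002101) / 0.002227 = −0.354, giving 36.2%.

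**5. Sensitivity at 3.5%.** 8,000 / 231,548 = 3.455%. This places all the deaths among the 2013 reported cases, so it mixes two sources.

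| Baseline | Design effect | Pairwise, two-sided | Pairwise, one-sided | A+B v C, two-sided | A+B v C, one-sided |
|---|---|---|---|---|---|
| 0.89% | 1 | 18.6% | 28.2% | 25.7% | 36.2% |
| 0.89% | 3.91 | 7.8% | 13.5% | 10.7% | 17.2% |
| 3.5% | 1 | 56.6% | 68.5% | 70.5% | 79.8% |
| 3.5% | 3.91 | 18.8% | 28.5% | 26.0% | 36.5% |

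The rows with design effect 1 are ceilings. The rows with 3.91 carry over the ICC from step 1, which is an assumption at a lower rate. The A+B columns are generous, because they credit Group B with the full effect although its CHWs use ChARM for four months and "then discontinue using ChARM and continue to monitor the respiratory rate visually using a timer only for the remaining 4 months".

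**6. Baseline needed for 80% power, no clustering.** 5.9% (pairwise, two-sided) down to 3.5% (A+B against C, one-sided). Clustering raises both.

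**The case against.** The 0.89% is a weak benchmark, and much of this case stands. It is a national ratio for all pneumonia episodes. The trial counts children brought to CHWs in areas more than 5 km from a CSCom, and the Background says that only 38% of symptomatic children reach an appropriate provider. Selection by severity and remoteness could raise fatality, while the inclusion of coughs and colds works the other way. The protocol does not settle the net direction. The paragraph behind the 0.89% is itself doubtful: "Pneumonia accounts for 2% of under-five deaths in Mali", set beside almost 8,000 pneumonia deaths, implies 8,000 / 0.02 = 400,000 under-five deaths a year, and the next page calls pneumonia the leading cause. The two Background statements on fatality can also both be true, since a rate may exceed 20% in some settings. Section 5 mentions a 2016 baseline survey that might hold a local rate, although Section 11 does not cite it.

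Three stronger readings are tempting, and the documents do not support them.
- A reader might infer that the trial's true power is 19%. The rate among cases seen by CHWs is not stated, so 19% only illustrates one baseline.
- A reader might infer that power is far below 80% under any comparison or sidedness. At 3.5%, without clustering, the one-sided test of A+B against C reaches about 80%.
- A reader might infer an arithmetic error. At 20% there is none.

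What does not stand is 20% as a supported average. Figure II tests it without the 0.89%, and the result is still about 1 in 22 covered under-fives dying of ARI in eight months.

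**Conclusion.** The concern holds as a fault in the baseline input. The 20% is unsourced, matches only an upper-range statement, and conflicts both with the national counts and with the number of children covered in the two districts. Without clustering, power for a 30% reduction runs from 19% to 36% at 0.89% and from 57% to 80% at 3.5%. At 3.5% with the clustering that makes the plan's pairwise two-sided 80% exact, it runs from 18.8% to 36.5%.

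These figures assume 2,400 cases per arm and the full 30% effect in every intervention arm compared. They show how strongly the claim depends on the baseline and do not estimate the trial's power. The point must be fixed, because this sentence is the only sample-size justification for the named primary outcome.

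**What to change.** In Section 11, Sample size, replace 20% with a sourced expected case-fatality rate for under-fives with cough and/or cold seen by CHWs. Alternatively, justify 20% against the Background counts and Figure II. Then state the expected deaths per arm and the power that the fixed sample size gives at that rate. If the rate does not support 80%, withdraw that claim for case fatality.

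The cost is a source and a rewritten sentence. Enrolment and outcomes stay as they are. The downside is a stated power that may be much less favourable.
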